Participating women will receive standardized self-awareness recommendations, although they will remain free to comply with them. They will be informed on potential risk-reducing strategies associated with their individual breast cancer risk level and individual risk factors. Upon risk calculation, they will receive a printed + online document summarizing all their personal information, risk category assignment, proposed screening strategy, but also suggested personalized risk-reduction measures (such as avoidance of certain endocrine therapies, dietary and exercise recommendations, etc). These measures have been predefined by the trial steering committee.

Participants will be able to retrieve all their personal information from their personal account on the study's web-platform. They also will be able to consult more general information on the project's website.

Table 2: **BREAST CANCER SCREENING SCHEME IN THE STANDARD ARM**

Standard arm (either no mammogram or mammogram(s)/1-2-3 years according to age and country – will be defined individually at study entry in the trial)				
Population	40-49 (France, Belgium, UK and Israel) 40-44 (All women of Italy) 45-49 (for some women depending the region of Italy)	50-70 (UK)	50-70 (France, Belgium, Italy and Israel)	45-49 (Some regions of Italy)
Planned images	No mammogram	Mammogram* every 3 years	Mammogram* every 2 years	Mammogram* every year

* Or Tomosynthesis + synthetic 2D if applicable in the country/center

Table 3: DEFINITION OF RISK THRESHOLDS IN MYPeBS AND **BREAST CANCER SCREENING SCHEME IN THE RISK-BASED ARM**

Risk-based arm				
Risk level	Low risk	Average risk	High risk	Very high risk
Numerical definition (invasive breast cancer risk at 5 years)	<1%	1-1.66%	$\geq 1.67\%$ and <6%	$\geq 6\%$ at 5 years
Mammogram*	1 at end of study	Every 2 years	Yearly	Yearly
Additional	Yearly breast cancer awareness reminder	High density: US or ABUS every 2 years	High density: US or ABUS every year	Annual MRI until age 60

* Or Tomosynthesis + synthetic 2D if applicable in the country/center

F) SAMPLES COLLECTED

SAMPLE TYPES: SALIVA SAMPLES

SAMPLE QUANTITIES: one sample of saliva at baseline for all women randomized into the risk-based screening arm

G) STUDY DURATION

[figure not shown]
INCLUSION PERIOD: 2.5 YEARS

STUDY FOLLOW-UP DURATION (FOR EACH WOMAN IN BOTH GROUPS): 4 YEARS

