1.1.15 MyPeBS population's anticipated age and risk structure

To make this trial feasible, the screening potential of each participating region/area has been carefully evaluated. Target accruals have been defined together. The recruitment will be competitive.

The realistic target age structure of women accrued in MyPeBS is: 25% aged 40-49, 45% aged 50-59, 30% aged 60-69. This age structure, as well as the risk structure in the risk-based arm, will be carefully and regularly scrutinized on order to allow potential recruitment adaptations. Monthly trial updates and steering committee meetings will be organized to allow this.

If the age and risk structure differs significantly from of initial plan, the study statistician, with the Clinical trial Steering Committee, together with the advice of the Ethics and data Monitoring Committee, will model these changes' effects on the initial statistical hypotheses and potentially propose an amendment of the study.

MyPeBS		women aged 40-49 (25%)	women aged 50-59 (45%)	women aged 60+ (30%)
risk level	average risk in level	Expected distribution	Expected distribution	Expected distribution
Low	0,8%	60%	28%	15%
average	1.4%	25%	33%	30%
high	2.3%	15%	40%	55%
TOTAL		10 625	19 125	12 750

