4. PARTICIPANTS' SELECTION

4.1 Inclusion criteria

Women from the general population (**only if they are invited by the national screening program or self-referred in a participating region of one of the participating countries**) will be eligible for the study if they fulfill all the following criteria (verified during the baseline phase and before randomization):

1. Female (whether born female or not)
2. Aged 40 to 70 years old (inclusive)
3. Willing and able to comply with scheduled visits, laboratory tests, and other trial procedures
4. Able to provide written informed consent obtained prior to performing any protocol-related procedures
5. Sufficient understanding of any of the languages used in the study
6. Affiliated to a social security/national healthcare system

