5.2.5 Breast Cancer Screening in the risk-based arm

In the risk-based arm, women are screened in a risk-based fashion:

Screening recommendations in each risk category are as described in the Table below.

- Women identified at low risk will not have any mammogram until an end of study mammogram at 4 years.
- Women at average risk will have a mammogram every 2 years
- Women at high risk will have a yearly mammogram
- Women at very high risk will have a yearly mammogram + yearly MRI until age 60. Both shall be performed at the same time period, MRI being performed before mammogram.
- Breast US is proposed in women with dense breasts, according to national guidelines

2D digital mammogram may be replaced by tomosynthesis according to the country's, regions' and centers' policy.

Definition of risk thresholds and breast cancer screening scheme in the **risk-based** arm are summarized below:

Risk-based arm				
Risk level	Low risk	Average risk	High risk	Very high risk
Numerical definition (invasive breast cancer risk at 5 years)	< 1%	1-1.66%	$\geq 1.67\%$ and < 6%	$\geq 6\%$ at 5 years
Mammogram*	1 at end of study	Every 2 years	Yearly	Yearly
Additional	Yearly breast cancer awareness reminder	High density: US or ABUS every 2 years	High density: US or ABUS every year	Annual MRI until age 60

* Or Tomosynthesis + synthetic 2D if applicable in the country/center

The participants' screening schedules will be organized according to the date of their last previous

mammogram, as described in the Table below:

		Planned initial Mammogram/ DBT schedule		
		Every 2 years	Yearly	Yearly
Schedule of first screening mammo/DBT according to previous mammogram	No previous mammogram	immediately	immediately	immediately
	Previous mammogram < 1 year	2 years from previous one	1 year from previous one	1 year from previous one
	Previous mammogram between 1 and 2 years	2 years from previous one	immediately	immediately
	Previous mammogram > 2 years	immediately	immediately	immediately

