8.2 Planned statistical analysis

8.2.1 Statistical analysis plan

A statistical analysis plan (SAP) describing in detail all statistical analyses performed will be elaborated. An intermediate progress report will be made after 1 year of inclusion to evaluate the robustness of the study with regards to estimated initial inclusion rates, expected age categories, risk predictions, and compliance to screening recommendations, on the overall population and at the country level to recommend potential changes to the protocol and/or study management. Indeed if the age and risk structure of the population appeared significantly different from those expected, with potential important influence on the study's power or ability to conclude, amendments may be proposed by the Clinical Trial Steering Committee, upon advice of the Ethics and data Monitoring Committee.

This progress report will be updated after 2 years of inclusion and during the follow-up period after the last woman randomization.

Beside this, the spread of SNPs chosen and harmonious population repartition will be verified after 5,000 women are included.

All the analyses for the progress reports will be conducted blinded from the efficacy outcomes of the study (breast cancer incidence). Once all the participants have been followed for 4 years, the cleaned database will be locked and a final statistical report prepared.

The primary analysis will compare the cumulative hazard functions of cancers of stage 2 + between the two randomized groups of women using a logrank test. The rate of cancers of stage 2 + cancers for each arm will be estimated as the number of cancers of stage 2 + detected either clinically or by screening out of the total person-years of follow-up.

The primary non-inferiority analysis will be performed on the per-protocol (PP) population, which will include all randomized and eligible women in the arm they were randomized to, who complied with their screening recommendation in terms of number of mammograms. The analyses will be repeated in the Intention-To-Treat (ITT) population for sensitivity. An additional sensitivity analysis, we will be performed using causal inference methods to estimate the average effect of the risk-based screening versus standard screening on stage 2 incidence as if all participants will have complied with the protocol.

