8.3 Study populations to be analysed

8.3.1 Definition of per-protocol population for the primary endpoint analysis

The per-protocol (PP) population will include all randomized and eligible women in the arm they were randomized to who complied with their screening recommendation.

Per-protocol definition of compliance (the study entry mammogram, if any, will not be considered) will be used for the primary analysis of the trial and is described below, according to randomization arm:

Per-protocol definition for standard arm:

Standard arm				
(either no mammogram or mammogram(s)/1-2-3 years according to age and country – will be defined individually at entry)				
Population	40-49 (France, Belgium, UK and Israel) 40-44 (All women of Italy) 45-49 (for some women depending the region of Italy)	50-70 (UK)	50-70 (France, Belgium, Italy and Israel)	45-49 (Some region of Italy)
Planned images	No mammogram	Mammogram every 3 years	Mammogram every 2 years	Mammogram every year
Per-protocol definition	≤ 1 mammogram over 4 years	≥ 1 mammogram over 4 years AND < 4 mammograms over 4 years (excluding diagnostic mammograms)	≥ 1 mammograms over 4 years AND < 4 mammograms over 4 years (excluding diagnostic mammograms)	≥ 2 mammograms over 4 years

Per-protocol definition for risk-based arm:

Risk-based arm				
	Low risk	Average risk	High risk	Very high risk
Planned images	Mammogram every 4 years +/- US if dense breast	Mammogram every 2 years +/- US if dense breast	Mammogram every year +/- US if dense breast	Mammogram + MRI every year for women < 60
Per-protocol definition (outside of baseline and end of study mammo)	≤ 1 mammograms over the 4 years	≥ 1 mammograms over 4 years AND < 4 mammograms over 4 years (excluding diagnostic mammograms)	≥ 2 mammogram over 4 years	≥ 3 mammograms over 4 years ≥ 3 MRIs over 4 years

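### The per-protocol rule for very-high-risk women asks for at least 3 MRIs with no age condition, although MRI is scheduled only until age 60; the effect on the primary analysis is probably small

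*Protocol*

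**What the plan says.** The primary non-inferiority test uses the per-protocol population, and the protocol describes compliance for that population in several places.

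- **Section 8.3.1, rule row, very-high-risk column:** "≥ 3 mammograms over 4 years" and, in the same cell, "≥ 3 MRIs over 4 years". Neither line carries an age condition.
- **Section 8.3.1, planned-images row of the same column:** "Mammogram + MRI every year for women < 60".
- **Section 8.3.1, lead sentence:** per-protocol women are those who complied with their own screening recommendation.
- **Section 8.2.1 (and the synopsis):** the population is women "who complied with their screening recommendation in terms of number of mammograms". MRI is not mentioned.
- **Section 5.2.5:** "Women at very high risk will have a yearly mammogram + yearly MRI until age 60". Synopsis Table 3 and the table in 3.1.4 agree ("Annual MRI until age 60").
- **Section 1.1.15:** the target age structure is "25% aged 40-49, 45% aged 50-59, 30% aged 60-69". Section 4.1 admits women up to age 70.

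**The concern.** The rule cell asks for more MRIs than the schedule gives to some of the women it governs. A very-high-risk woman who enters at 62 and attends every yearly mammogram has done all that was asked of her. She has no scheduled MRI, so on the literal rule she fails. Under 8.2.1 the same woman is compliant. The document therefore supports two different primary analysis sets.

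The misclassification is one-sided. Risk is estimated only in the risk-based arm, so comparable women in the standard arm are not identified and are judged on mammogram counts. The women lost have a 5-year risk of 6% or more. Losing them lowers the stage 2+ rate of the experimental arm, which favours non-inferiority. That result also gates the superiority test. In an open-label trial, a choice between two readings is better settled before the per-protocol set is derived.

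**Working it through.** **1. The plan's own figure.** Section 8.1 requires 298 events (margin 1.25, assumed ratio 0.9, one-sided 2.5%, 80% power). With θ = 0.9/1.25 = 0.72 and (1.960 + 0.842)² = 7.849:
- Freedman: ((1 + 0.72)/(1 − 0.72))² × 7.849 = 296.2, so 297.
- Schoenfeld: 4 × 7.849/(ln 0.72)² = 290.9, so 291.

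The 298 is reproduced to within 3%, and this point does not change it.

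**2. Who cannot reach 3 scheduled MRIs.** With yearly MRI before age 60 and the first one *f* years after entry, the third falls at entry age + *f* + 2. It is scheduled only if entry age < 58 − *f*. Risk results come 8 to 12 weeks after entry (*f* about 0.25). Under the 5.2.5 scheduling table a recent mammogram can push the first round to about 12 months (*f* = 1).

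| Entry age | MRIs scheduled, *f* = 0.25 | MRIs scheduled, *f* = 1 |
|---|---|---|
| 56 | 4 | 3 |
| 57 | 3 | 2 |
| 58 | 2 | 1 |
| 59 | 1 | 0 |
| 60 or over | 0 | 0 |

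The cut-off is entry at 57.75 (*f* = 0.25) or 57 (*f* = 1). From 60 upwards no MRI is scheduled.

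**3. How many women.** The protocol gives no very-high-risk share, and the planning tables in 1.1.15 and 1.2.2.1 have no such row. I assume 0.2% to 2% of 42,500. As partial anchors, 1.1.22 puts high-penetrance variants at no more than 1 in 500 in general populations. It also gives founder mutations as 3% in Ashkenazi women; applied to all 7,500 Israeli women in one arm, that is at most 225 women (0.5% of the arm). The affected age share is 30% (60+), or 30% + 2/10 × 45% = 39% (58+, ages spread evenly within 50–59).
- Low: 42,500 × 0.002 × 0.30 ≈ 26 women.
- High: 42,500 × 0.02 × 0.39 ≈ 332 women.

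**4. How many events.** Assume a 5-year risk of 6%, 4/5 of it within 4 years, and 25% at stage 2+ (section 1.1.2): 0.06 × 0.8 × 0.25 = 1.2% per woman.
- Low: 26 × 0.012 ≈ 0.3 events.
- High: 332 × 0.012 ≈ 4 events.
- Extreme: 2% prevalence, 60% aged 58+, and a 38% stage 2+ share (204 expected stage 2+ events over 530 cancers). That is 42,500 × 0.02 × 0.60 = 510 women and 510 × 0.048 × 0.38 ≈ 9.3 events.

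**5. Effect at the non-inferiority boundary.** The 4-year hazard is 4 × 120/100,000 = 0.0048. Per-protocol shares are 70% and 90%; drop-out is ignored.
- Standard arm: 42,500 × 0.70 × 0.0048 = 142.8 events.
- Risk-based arm at a true ratio of 1.25: 38,250 women, 38,250 × 0.0048 × 1.25 = 229.5 events.

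Apparent ratio = [(229.5 − events lost)/(38,250 − women lost)]/0.0048. Error = 1 − Φ(1.96 − ln(1.25/apparent ratio)/SE), with SE = √(1/risk-based events + 1/142.8).

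| Case | Women lost | Events lost | Apparent ratio | One-sided error |
|---|---|---|---|---|
| 0.2%, 60+ | 26 | 0.3 | 1.249 | 2.5% |
| 0.5%, 58+ | 83 | 1.0 | 1.247 | 2.6% |
| 2%, 58+ | 332 | 4.0 | 1.239 | 3.0% |
| 2%, 60% aged 58+, 25% stage 2+ | 510 | 6.1 | 1.233 | 3.3% |
| Same, 38% stage 2+ | 510 | 9.3 | 1.215 | 4.5% |

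**6. Direction and power.** At the boundary the arm average is 0.0048 × 1.25 = 0.6%, against 1.2% for the women lost. The direction would reverse only if their stage 2+ share fell below 0.6/4.8 = 12.5%. Losing 4 of about 293 expected events (with 5% drop-out) moves power from 79.6% to 79.1%.

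**The case against.** The text can be read more kindly. The age limit in the planned-images row may be meant to carry down to the rule below it, and the lead sentence of 8.3.1 would keep a woman who followed her own recommendation. If 8.2.1 governs, MRI does not count at all. A reader might therefore infer too much by saying that compliant women will certainly be removed. The documents do not establish that: an MRI done outside the schedule would count, and for women of 57 to 59 the outcome depends on the first MRI date and on how the age-60 limit is applied. What stands is that the rule cell carries no age condition, gives no threshold to a woman who turns 60 during follow-up, and conflicts with 8.2.1. Benign intent does not repair it.

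A reader might also infer serious inflation of the type I error. Setting about 9 lost events against some 165 risk-based events suggests an apparent ratio near 1.19 and an error near 6.5%. But 165 is the count under the alternative (42,500 × 0.9 × 0.0048 × 0.9). At the boundary the arm has about 230 events, and the women lost take their person-years with them. The same extreme inputs then give about 1.215 and 4.5%. Those inputs are themselves doubtful: the planning tables leave no room for a very-high-risk group, section 4.2 excludes known or suspected carriers, and the 38% stage share includes women under 50 with no planned mammogram.

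The intention-to-treat sensitivity analysis and the superiority test do not use this rule. Even 510 women are 1.2% of the arm, against planned non-compliance of 10% and 30%.

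**Conclusion.** Wrong as written; minor to moderate. On its literal text, the very-high-risk cell in 8.3.1 counts as non-compliant some women who followed their schedule: those aged 60 or over at entry, and those who turn 60 before a third scheduled MRI. It does so in the risk-based arm only, in the direction that favours non-inferiority, and against the compliance definition in 8.2.1. The effect on the primary result is probably small: about 0.3 to 4 stage 2+ events, with one-sided error between about 2.5% and 3.0%. Only stacked extreme assumptions bring it to about 4.5%. All these sizes rest on an assumed very-high-risk prevalence and stage share. The contradiction itself rests on no assumption. The documents do not support calling this a serious threat to the trial's conclusion.

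**What to change.** Reconcile 5.2.5, 8.2.1 and 8.3.1 before the per-protocol set is derived:

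- In 8.3.1, express the MRI criterion as MRIs attended against MRIs scheduled for that woman during follow-up, and judge women with none scheduled on mammograms alone.
- State for women who turn 60 during follow-up how many scheduled MRIs they must attend.
- Use one compliance definition in 8.2.1, 8.3.1 and the synopsis, saying whether MRI counts.

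The cost is one clause in 8.3.1 and a matching sentence in 8.2.1 and the synopsis. The event target and sample size stay as they are. The change concerns only how compliance is counted; it alters no screening schedule and takes no position on when MRI should stop.

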8.3.2 Definition of intent to treat population for the main secondary endpoint analysis

Intent to treat population comprises all women randomized to either study arm and evaluable for the main secondary endpoint analysis, whatever was their compliance with the screening schedule they were assigned to.

8.4 Interim analyses

No interim analyses of the primary endpoint are planned.

Intermediate analysis of the secondary socio-psychological endpoints will be performed at year 1 and then on a yearly basis to verify that there is not detrimental psychological impact of the risk assessment and/or participation in the protocol. The results of these yearly evaluations will be examined by the trial steering committee as well as the Ethics and Data Monitoring Committee.

8.5 Definition of events for final analysis

Events considered for incidence rate of stage 2 + breast cancers are:

- **Stage 2, 3 or 4 invasive primary breast adenocarcinoma** occurring from the day of randomization until 4 years from this day (defined from UICC 2010 classification, which means including all T2, T3 and T4 adenocarcinomas carcinomas, and/or carcinomas with lymph node involvement > pN1a)
- Death related to breast cancer that occurred without a prior breast cancer diagnosis

The following lesions are NOT considered as events:

- Adenocarcinomas of stage 0 or 1 (of note, T1pN0i+ and pN1mi lesions are classified as stage 1)
- In situ adenocarcinomas
- Non primary breast adenocarcinomas (of metastatic origin)
- Breast tumours that are not adenocarcinomas including lymphomas or sarcomas
- Deaths not related to breast cancer

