Tumor stage remains of high prognostic impact in patients with early breast cancer, both at short and long term. As an illustration, in the recent, very large, European breast cancer clinical trial Mindact (Cardoso et al 2016) in which four of the 5 MyPeBS countries participated, T stage remained one of the two major prognostic factors, with a hazard ratio (HR) of 1.92 for distant metastasis-free survival at 5-years (the other one being genomic risk assessment, HR 2.41). Tumor stage is of major impact at short term for ER-negative breast cancer (HR, in which metastatic risk is almost limited to the initial 5-6 years from diagnosis). Tumor stage is however, also associated with a major long-term prognostic impact in ER+ breast cancer patients. In the 20-year analysis of ER-positive breast cancer patients included in the major randomized trials (Pan et al 2017), T stage remains a major prognostic factor at long term: T1 tumors are associated with long-lasting annual risks around 1%, while it is around 1.5% for T2, and much higher for T3 and 4. Nodal status retains the most important prognostic impact. Overall, the HR of distant metastases for stage 1 as compared to T2N0 is 0.49 years 0-5 versus 0.70 years 5-20; but stages T1N1-3 to T2N4-9 (all stage 2 and higher) are associated with a HR of long-term relapse between 1.19 and 2.63 as compared to T2N0.

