3.2 Study Endpoints

3.2.1 Primary endpoint

The primary endpoint is the incidence rate of stage 2 + breast cancers at 4 years (UICC 2010)

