Further assumptions are a non-inferiority margin of a 25% relative increase in the risk-based arm (null hypothesis $H_0: \lambda_e/\lambda_c \geq 1.25$ with t and c standing for experimental and standard arm, respectively; it corresponds to an absolute increase in the cumulative hazard rate of stage 2 cancer or higher after 4 years up to 120/100000 stage 2 cancers the risk-based arm under H_0), 80% power, 2.5% significance level, 1-sided test. If we assume that under the alternative hypothesis a 10% relative improvement can be expected by the experimental risk-based-stratified screening arm (i.e. $\lambda_e/\lambda_c = 0.9$) due to our anticipated increase in the average numbers of mammograms in the experimental arm, a total of 298 stage 2 breast cancers are required for the non-inferiority assessment using a logrank test. We assume a total of 85,000 participants, 42,500 in each arm, to be included over 2.5 years.

For the primary and key secondary endpoint analysis, each subject will be followed for four years, to be able to compare cycles of mammograms between the 2 screening arms. Later updates of the trial analyses will be performed using longer follow-up.

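### The primary-event definition contradicts itself on T1 pN1a cancers: UICC 2010 stage 2 to 4 counts them, but the T/N test given as its meaning omits them

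*Protocol*

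**What the plan says.** Section 8.5 lists the events for the primary analysis. The governing words are "Stage 2, 3 or 4 invasive primary breast adenocarcinoma", tied to UICC 2010. A parenthesis in the same bullet then gives what that classification is taken to mean: "including all T2, T3 and T4 adenocarcinomas carcinomas, and/or carcinomas with lymph node involvement > pN1a".

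The non-event list in section 8.5 removes stages 0 and 1 and adds "of note, T1pN0i+ and pN1mi lesions are classified as stage 1". It does not mention pN1a.

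Section 3.2.1 defines the endpoint by stage alone, under UICC 2010, with no nodal rule. Section 1.1.13, which justifies stage 2+ as a surrogate, refers to "stages T1N1-3 to T2N4-9 (all stage 2 and higher", so it treats T1 disease with N1 nodes as stage 2+. Nothing elsewhere in the protocol corrects the sign in section 8.5.

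**The concern.** Section 8.5 is the only place where the protocol turns stage 2+ into a concrete test on T and N. A T1 pN1a cancer is not T2 to T4, and its nodal status is not greater than pN1a, so it fails both limbs. It is also not among the node-positive categories held at stage 1. On the literal test it falls between the two lists.

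The objective, the endpoint, the 120 per 100,000 per year control rate and the 298 required events all refer to stage 2+ as a whole. If the event derivation followed the parenthesis, the trial would count a narrower set of cancers than the one it was sized on. Section 1.1.13 also rests the surrogate partly on the prognostic weight of nodal status, so leaving out a node-positive category would weaken that argument. The trial is open-label, so event status should not depend on which half of a sentence is read.

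**Working it through.** **The texts side by side, for a T1 pN1a cancer**

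| Source | Result |
|---|---|
| Section 8.5, stage clause (UICC 2010 stage 2 to 4) | event |
| Section 8.5, T/N test (above pN1a) | not an event |
| Section 8.5, stage 1 note (only T1 pN0(i+) and pN1mi) | not held at stage 1 |
| Section 1.1.13 (T1N1-3 is stage 2 or higher) | stage 2+ |

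Three of the four agree; only the T/N test differs. Reading pN1a as the category with 1 to 3 involved nodes is standard TNM notation. It fits the node counts N1-3 and N4-9 in section 1.1.13. The stage 1 note points the same way: it puts the cut just above pN1mi, not above pN1a.

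**The protocol's event requirement**

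Inputs from section 8.1: "non-inferiority margin of a 25% relative increase in the risk-based arm"; "under the alternative hypothesis a 10% relative improvement can be expected" (hazard ratio 0.9); "80% power, 2.5% significance level, 1-sided test". The effective ratio is 0.9 / 1.25 = 0.72, and (1.96 + 0.8416)² = 7.849.

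- Freedman: 7.849 × (1.72 / 0.28)² = 296.2, so 297.
- Schoenfeld, 1:1: 4 × 7.849 / (ln 0.72)² = 290.9, so 291.

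The stated 298 is reproduced to within 1 event (Freedman) or 2.3% (Schoenfeld). It depends on margin, effect, alpha and power, not on which cancers count.

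**Expected per-protocol events if all stage 2+ cancers count**

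Inputs from section 8.1: 42,500 women per arm, 4 years, 0.0012 per year in the standard arm, drop-out taken at its 5% ceiling, non-compliance 30% (standard) and 10% (risk-based).

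- Standard: 42,500 × 0.95 × 0.70 × 4 × 0.0012 = 135.7
- Risk-based: 42,500 × 0.95 × 0.90 × 4 × 0.0012 × 0.9 = 157.0
- Total: 292.6, about 293 (289 to 308 depending on how drop-out is applied)

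There is little reserve above 298.

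**Illustration if T1 pN1a is left out**

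The protocol gives no T1 pN1a share, so 10 to 30% is an assumption. It is taken as equal in both arms, with the hazard ratio still 0.9. Power = Φ(½ × √D × ln(1.25 / 0.9) − 1.96), with ln(1.25 / 0.9) = 0.3285.

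| Assumed share | Expected events D | Power |
|---|---|---|
| 0% | 292.6 | 0.80 |
| 10% | 292.6 × 0.9 = 263.4 | 0.76 |
| 20% | 292.6 × 0.8 = 234.1 | 0.71 |
| 30% | 292.6 × 0.7 = 204.8 | 0.65 |

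**The case against.** The strongest reply is that the stage clause governs and the parenthesis only explains it. Sections 3.2.1 and 8.5 both name UICC 2010, the non-event list removes only stages 0 and 1, and the explanation opens with a word that can be read as non-exhaustive. On that reading T1 pN1a is an event and no cancer is lost. This largely stands. A reader might infer that these cancers are excluded and that the trial tests a different endpoint from the one it powers, but the protocol does not support that: section 8.5 points both ways.

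Other parts of the reply also stand:

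- It would be wrong to say that the 298 falls. It is a requirement, not a yield; only the expected count could fall.
- The power figures have no anchor in the protocol, because the T1 pN1a share is not given.
- One might infer that sites will code the same cancer differently. Section 11.1.2 says that cancer events come from women, investigators, screening centres and insurance databases. It does not say who applies the section 8.5 test, so this is a possibility and no more.
- Section 1.1.13 is background on a cited analysis and does not use the term pN1a. It supports the reading but does not define the event.

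A misprinted sign is possible. The greater-or-equal sign appears intact elsewhere, including section 8.3.1, so this cannot be assumed.

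What does not stand is that the point can be left alone. The parenthesis is offered as the meaning of the stage rule and is the only concrete T/N test for the primary event. On T1 pN1a it disagrees with the rule it explains.

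**Conclusion.** Wrong as written: an internal inconsistency in the primary-event definition. Nothing in the protocol suggests a deliberate choice to leave out T1 pN1a, and the pN1mi note suggests a drafting slip.

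The contradiction rests on the text and on the ordinary meaning of pN1a. Its effect is conditional. If events are taken by UICC stage, nothing is lost. If the literal test is used, expected per-protocol events fall below about 293 by the T1 pN1a share, which is unknown here. The range of 0.76 to 0.65 for power is illustrative and should not be quoted as an estimate.

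**What to change.** Either of two corrections in section 8.5 would do:

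- change the nodal limb to pN1a or higher, that is, any nodal involvement above pN1mi; or
- delete the parenthesis and define events solely as UICC 2010 stage 2 to 4.

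The second also covers a T1 node-negative cancer with distant metastasis, which is stage 4 under the head clause but is not named in the parenthesis. Under the first, that case should be added.

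Keep T1 pN0(i+) and T1 pN1mi as non-events, and check that the event derivation uses the same rule.

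The cost is a short text correction and that check, with no new data. It does need a protocol amendment, with the approvals that section 13.5 requires before it is implemented.
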